5.4 Investigational Imaging Agent Administration

10 millicurie (mCi) of ¹⁸F-fluciclovine will be administered via slow push over 10 seconds through a peripheral intravenous line. [33]. This is performed immediately prior to imaging. No specific pre-administration lab parameters or procedures for the patient is required prior to agent administration.

5.4.1 Image Acquisition Details:

Immediately after the injection of the radiopharmaceutical, dynamic PET/CT images of the pelvis will be obtained for 15 minutes. Subsequently, PET/CT images will be obtained from the pelvis to the base of skull in the caudal to cranial direction. CT will be obtained for attenuation correction per standard institutional PET/CT policies. PET images will be acquired in 3D mode at 3-5 minutes per bed position.

As noted in Section 8.1, this image acquisition protocol is based on the pharmacokinetics of the agent in male patients with prostate cancer. While we do not anticipate significant differences in the kinetics of the agent in patients with bladder cancer, appropriate adjustments to the imaging acquisition parameters will be made if significant differences are observed on initial imaging studies.

5.4.2 Image Analysis Details:

¹⁸F-fluciclovine-PET/CT images will be reviewed for lesions, defined as focal areas of ¹⁸F-fluciclovine uptake not correlating with normal anatomy or physiology. Lesions will be scored on a 5-point scale for diagnostic certainty (0, definitely benign; 1, probably benign; 2, equivocal; 3, probably malignant; and 4, definitely malignant).

Three-dimensional regions of interest will be placed in areas of abnormal tracer uptake scored as 3-5 and the level of ¹⁸F-fluciclovine uptake recorded. Measures of ¹⁸F-fluciclovine will include: maximal standardized uptake value (SUV_{max}, body weight), metabolic tumor volume (MTV; volume of tumor [cm³] with SUV >42% of SUV_{max}), SUV_{mean} (within the MTV), and total lesion avidity (TLA; calculated as MTV × SUV_{mean}). Tumor to background ratios will also be calculated using blood pool, muscle and bone marrow as reference normal organs.

5.5 Duration of Study Participation

Duration of study participation will be until the time that surgical specimens are obtained at the time of radical cystectomy.

Participants may be removed from study participation prior to the scheduled completion if one of the following events occurs:

- Unacceptable adverse event(s),
- Participant demonstrates an inability or unwillingness to comply with the study procedures,
- Participant decides to withdraw from the study,
- Condition that would result in confounding information for study procedure interpretation as determined by the study investigators,
- General or specific changes in the participant's condition render the participant unacceptable for continuing study procedures in the opinion of the treating investigator.

5.6 Duration of Follow Up

After completing the study procedures, patients will be followed for at least 30 days. Continued standard of care will be provided by the treating physician. Participants removed from the study for unacceptable adverse events determined to be related to the study drug will be followed until resolution or stabilization of the adverse event.

5.7 Criteria for Taking a Participant Off Study

Participants will be removed from study when any of the following criteria apply:

- Lost to follow-up
- Withdrawal of consent for data submission
- Death

The reason for taking a participant off study, and the date the participant was removed, must be documented in the case report form (CRF). In addition, the study team will ensure Off Treatment/Off Study information is updated in OnCore in accordance with DF/HCC policy REGIST-101. If a participant is taken off study prior to undergoing the research ¹⁸F-fluciclovine-PET/CT scan, the participant may be replaced.

6. DOSING DELAYS/DOSE MODIFICATIONS

Dose delays and modifications will be made as indicated in the following table(s). The descriptions and grading scales found in the revised NCI Common Terminology Criteria for Adverse Events (CTCAE) version 4.0 will be utilized for dose delays and dose modifications. A copy of the CTCAE version 4.0 can be downloaded from the CTEP website http://ctep.cancer.gov/protocolDevelopment/electronic_applications/ctc.htm.

If possible, symptoms should be managed symptomatically. In the case of toxicity, appropriate medical treatment should be used (including anti-emetics, anti-diarrheals, etc.).

The study procedure is ¹⁸F-fluciclovine PET/CT imaging. All adverse events experienced by participants will be collected from the time of the administration of the study agent (¹⁸F-fluciclovine) until 24 hours after ¹⁸F-fluciclovine PET/CT images are obtained, regardless of their attribution/relatedness). Adverse events related to standard-of-care of FDA-approved procedures for comparison with ¹⁸F-fluciclovine PET/CT imaging (i.e., Diagnostic CT scans, MR imaging) will not be reported as part of this trial. Beyond 24 hours after ¹⁸F-fluciclovine PET/CT imaging, adverse events that are determined to be related to the participant's systemic therapy or underlying condition and are determined not to be related to the agents and procedures in this protocol, will not be reported, as the investigational procedure is a diagnostic imaging procedure.

Adverse events related to radical cystectomy surgery will not be reported as part of this trial. Participants continuing to experience toxicity related to ¹⁸F-fluciclovine at the off-study visit may be contacted for additional assessments until the toxicity has resolved or is deemed irreversible.

6.1 Anticipated Toxicities

6.1.1 Expected Adverse Events from ¹⁸F-fluciclovine

¹⁸F-fluciclovine will be administered in tracer quantities. As such, the tracer dose of ¹⁸F-fluciclovine is expected to have no significant effect on normal human physiology and we do not anticipate any adverse events [36].

¹⁸F-fluciclovine is an FDA-approved imaging agent for evaluation of metastatic prostate cancer. Adverse reactions were reported in $\leq 1\%$ of subjects during clinical studies with Axumin (Appendix B). The most common adverse reactions were injection site pain, injection site

erythema and dysgeusia. To date, no adverse events have been reported that have been directly attributable to ¹⁸F-fluciclovine [36],

6.1.2 Expected Adverse Events from Intravenous Line Placement

- Minor discomfort
- Bleeding at the injection site
- Infection at the injection site
- Bruising at the injection site
- Claustrophobia
- Discomfort

6.1.3 Expected Adverse Events from Radiation from PET/CT scans

The estimated effective dose from ¹⁸F-fluciclovine is approximately effective dose per unit administered activity is 22.1 μ Sv/MBq [44].

Additional exposure from the CT component of the combined ¹⁸F-fluciclovine PET/CT scan is approximately 10 mSv.

| Table 1. Dosimetry for ¹⁸F-fluciclovine [44] | |
|--|---------------------------------|
| Organ | (μGy/MBq) |
| Liver | 33.5\pm4.2 |
| Kidneys | 13.7\pm0.8 |
| Spleen | 23.8\pm11.7 |
| Bladder wall | 25.2\pm17 |
| Lungs | 34.5\pm5.3 |
| Whole body | 12.6\pm0.2 |
| Effective dose | 22.1\pm2.1 |

6.2 Toxicity Management

Allergic reactions and anaphylaxis to ¹⁸F-fluciclovine will be managed following standard institutional guidelines for contrast reaction management (DFCI Department of Imaging Policy 5.31).

If a study participant has a severe allergic reaction or anaphylactic reaction to ¹⁸F-fluciclovine and PET/CT images are unable to be obtained, the participant will be removed from the study.

All other toxicities and adverse events will be managed as medically necessary. Supportive care will be administered as medically necessary.

6.3 Dose Modifications

The dosage of ¹⁸F-fluciclovine is never modified.

7. ADVERSE EVENTS: LIST AND REPORTING REQUIREMENTS

Adverse event (AE) monitoring and reporting is a routine part of every clinical trial. The following list of reported and/or potential AEs (Section 7.1) and the characteristics of an observed AE (Section 7.2) will determine whether the event requires expedited reporting **in addition** to routine reporting.

7.1 Expected Toxicities

Local injection site pain
Local injection site erythema
Dysgeusia

7.2 Adverse Event Characteristics

- **CTCAE term (AE description) and grade:** The descriptions and grading scales found in the revised NCI Common Terminology Criteria for Adverse Events (CTCAE) version 4.0 will be utilized for AE reporting. All appropriate treatment areas should have access to a copy of the CTCAE version 4.0. A copy of the CTCAE version 4.0 can be downloaded from the CTEP web site
http://ctep.cancer.gov/protocolDevelopment/electronic_applications/ctc.htm.
- **For expedited reporting purposes only:**
 - AEs for the agent(s) that are listed above should be reported only if the adverse event varies in nature, intensity or frequency from the expected toxicity information which is provided.
 - Other AEs for the protocol that do not require expedited reporting are outlined in the next section (Expedited Adverse Event Reporting) under the sub-heading of Protocol-Specific Expedited Adverse Event Reporting Exclusions.
- **Attribution of the AE:**
 - Definite – The AE is *clearly related* to the study treatment.
 - Probable – The AE is *likely related* to the study treatment.
 - Possible – The AE *may be related* to the study treatment.
 - Unlikely – The AE is *doubtfully related* to the study treatment.
 - Unrelated – The AE is *clearly NOT related* to the study treatment.

7.3 Adverse Event Reporting

7.3.1 In the event of an unanticipated problem or life-threatening complications treating investigators must immediately notify the Overall PI.

7.3.2 Investigators **must** report to the Overall PI any adverse event (AE) that occurs after the initial dose of study treatment, during treatment, or within 30 days of the last dose of treatment on the local institutional SAE form.

7.3.3 DF/HCC Adverse Event Reporting Guidelines

Investigative sites within DF/HCC will report AEs directly to the DFCI Office for Human Research Studies (OHRS) per the DFCI IRB reporting policy.

7.3.4 Protocol-Specific Adverse Event Reporting Exclusions

For this protocol only, the AEs/grades occurring from the time of ¹⁸F-fluciclovine administration until 24 hours after ¹⁸F-fluciclovine administration will be reported. However, they still must be reported through the routine reporting mechanism (i.e. case report form).

7.4 Reporting to Hospital Risk Management

Participating investigators will report to their local Risk Management office any participant safety reports, sentinel events or unanticipated problems that require reporting per institutional policy.

7.5 Routine Adverse Event Reporting

All Adverse Events **must** be reported in routine study data submissions to the Overall PI on the toxicity case report forms. **AEs reported through expedited processes (e.g., reported to the IRB, FDA, etc.) must also be reported in routine study data submissions.**

7.6 Additional Adverse Event Reporting

In addition to the reporting of Adverse Events as described in 7.5, any observed Serious Adverse Events that occur following the receipt of ¹⁸F-fluciclovine, whether related to the product or not, PI or designee shall notify BED within twenty four (24) hours of knowledge of any SAEs. SAE reports to BED must be recorded and faxed or scanned and emailed to::

Bracco Diagnostics Inc. Drug Safety Unit
E mail: [contact]
[contact]

8. IMAGING AGENT INFORMATION

A list of the adverse events and potential risks associated with ¹⁸F-fluciclovine can be found in Section 7.1 and Appendix B

8.1 ¹⁸F-fluciclovine

8.1.1 Description

¹⁸Fluorine-Fluciclovine is (1r, 3r)-1-amino-3[¹⁸F]fluorocyclobutane-1-carboxylic acid. The molecular weight is 132.1.

The following pharmacokinetic information for ¹⁸F-fluciclovine is based on experience in male patients with prostate cancer:

Following intravenous administration, ¹⁸F-fluciclovine distributes to the liver (14% of administered activity), pancreas (3%), lung (7%), red bone marrow (12%) and myocardium (4%). With increasing time, ¹⁸F-fluciclovine distributes to skeletal muscle.

Following intravenous administration, the tumor-to-normal tissue contrast is highest between 4 and 10 minutes after injection, with a 61% reduction in mean tumor uptake at 90 minutes after injection.

Across the first four hours post-injection, 3% of administered radioactivity is excreted in the urine. Across the first 24 hours post-injection, 5% of administered radioactivity is excreted in the urine.

It should be noted that the pharmacokinetics of ¹⁸F-fluciclovine is unknown in patients with bladder cancer at this time, and may not follow the distribution pattern described above. While we do not anticipate significant differences for bladder cancer patients, appropriate adjustments to the imaging parameters will be made as necessary if this pattern is dramatically different on initial studies.

8.1.2 Form

¹⁸F-fluciclovine is supplied as a clear, colorless injection in a ready to use syringe that contains a single patient-specific dose of ¹⁸F-fluciclovine at calibration time and date. ¹⁸F-fluciclovine is supplied by PETNET for Blue Earth Diagnostics Ltd. Prior to study opening, Blue Earth Diagnostics will work with Dana Farber Cancer Institute and PETNET to set up a study-specific account for this trial. This account should be used for ordering doses for the study. The BED study number (BED-IIT-355) should be referenced when ordering doses.

8.1.3 Storage and Stability

¹⁸F-fluciclovine is stored at controlled room temperature (USP) 20°C to 25°C (68°F to 77°F). ¹⁸F-fluciclovine does not contain a preservative. ¹⁸F-fluciclovine is stored within the original container in radiation shielding.

8.1.4 Compatibility

¹⁸F-fluciclovine is being administered in this study in tracer quantities for diagnostic imaging purposes. No drug interactions are expected between ¹⁸F-fluciclovine and other drug regimens that each patient may be receiving.

8.1.5 Handling

¹⁸F-fluciclovine should be handled and administered only by nuclear medicine personnel trained to handle radioactive material.

8.1.6 Availability

¹⁸F-fluciclovine will be provided by Blue Earth Diagnostics Ltd as part of a research agreement for this study.

8.1.7 Administration

10 millicurie (mCi, ± 20%) of ¹⁸F-fluciclovine will be administered via slow push over 10 seconds intravenously. A peripheral IV line is preferred. A butterfly line or established IV line may be used as long as the patency is established. The use of a power port needs to be approved by the study team.

8.1.8 Ordering

The study investigators will order the ¹⁸F-fluciclovine from PETNET per institutional policies for the ordering of radiopharmaceuticals. Prior to study opening, Blue Earth Diagnostics will work with Dana Farber Cancer Institute and PETNET to set up a study-specific account for this trial. This account should be used for ordering doses for the study. The BED study number (BED-IIT-355) should be referenced when ordering doses.

8.1.9 Accountability

A computer-based system for logging receipt and administration of radiopharmaceuticals per DFCI Imaging/Nuclear Medicine will be used for the accountability of the unit doses of the study radiopharmaceutical, ¹⁸F-fluciclovine, received from Blue Earth Diagnostics, Ltd.

8.1.10 Destruction and Return

Unused ¹⁸F-fluciclovine will be disposed of following institutional policies for the disposal of radioactive waste.

BIOMARKER, CORRELATIVE, AND SPECIAL STUDIES

Correlation of imaging data with pathological specimens obtained at the time of radical cystectomy will be performed as described in Sections 2.5, 5.3 and 13.2.

10. STUDY CALENDAR

| Phase | Pre-study | Study day | After Study |
|--|-----------|-------------------------------------|-------------|
| | | Within 6 weeks of Diagnostic CT/MRI | |
| Obtain informed consent | x | | |
| Review inclusion/exclusion criteria | x | | |
| Physical exam ¹ | x | | |
| Review of prior/concomitant medications ¹ | x | x | |
| Qualitative β -hCG | x^5 | | |
| Height/weight ² | | x | |
| ^{18}F -Fluciclovine PET/CT | | x | |
| Diagnostic CT/ MRI | x^1 | | |
| Collection of surgical specimens | | | x^6 |
| Review adverse events ⁴ | x | x | |

¹Physical exams, review of prior/concomitant medications, serum creatinine, serum or urine β -hCG at baseline, vital signs as part of the physical exam, and diagnostic CT/MRI obtained pre-study are part of the standard-of-care for patients with bladder cancer. We will be collecting and reviewing the data from these standard procedures to compare to ^{18}F -fluciclovine PET/CT imaging

results. Those with ECOG performance status ≤ 2 (Karnofsky $\geq 60\%$, see Appendix A) will be eligible. A urine pregnancy test will be performed where indicated.

²Height and weight will be obtained as part of the PET/CT scan procedures.

⁴Adverse events will be collected from the time of administration of ¹⁸F-fluciclovine until 24 hours after ¹⁸F-fluciclovine-PET/CT imaging.

⁵Female participants of childbearing potential must have a negative qualitative pregnancy test (β -hCG) at the Study Day. Results of a standard-of-care β -hCG may be used for the injection of ¹⁸F-fluciclovine if performed within 24 hours prior. Females who are two years post tubal ligation or postmenopausal for at least one year are not considered to be of childbearing potential and do not need to undergo pregnancy testing.

⁶ This is part of the standard-of-care radical cystectomy.

MEASUREMENT OF EFFECT

11.1 Pathological staging of bladder cancer

Pathological staging of bladder cancer is not the primary objective of this study. It will be used for comparison and correlation with imaged-based staging on ¹⁸F-fluciclovine PET/CT and standard-of-care MRI and diagnostic CT.

DATA REPORTING / REGULATORY REQUIREMENTS

Adverse event lists, guidelines, and instructions for AE reporting can be found in Section 7.0 (Adverse Events: List and Reporting Requirements).

12.1 Data Reporting

12.1.1 Method

The study team in the Department of Imaging will collect, manage, and perform quality checks on the data for this study.

The following databases will be utilized:

- Partners' Research Patient Data Registry (RPDR) – Clinical database that indexes results from the Partners' hospitals, including BWH. This will be used to augment the pathology and laboratory data from the CRIS database.
- Epic – Epic will be used to collect patient medical history as detailed in the "Methods of Data Collection" section below.

- Centricity Patient Archiving and Communication Systems (PACS) – Radiology system for SOC image storage as well as only anatomical imaging analysis on fluciclovine PET/CT studies. This system will be used by the study radiologists to collect and analyze subjects' imaging data and gather tumor measurements.
- Hermes PACS – DFCI Imaging PACS for all of Nuclear Medicine, PET/CT, and non-SOC data of all imaging modalities that can't be stored on Centricity. All fluciclovine project data, including data received from outside hospitals, will be placed into a dedicated archive on Hermes. This data will be read from Hermes storage using Hermes viewing/analysis software.
- DFCI Imaging PET/CT database – A database of patient information and scanning parameters. The database contains data for all PET and PET/CT acquisitions performed at DFCI Imaging. It will be used to retrieve this information when it is needed.

12.1.2 Responsibility for Data Submission

Investigative sites within DF/HCC or DF/PCC are responsible for submitting data and/or data forms to the Office of Data Quality (ODQ) in accordance with DF/HCC policies

12.2 Data Safety Monitoring

The DF/HCC Data and Safety Monitoring Committee (DSMC) will review and monitor toxicity and accrual data from this study. The committee is composed of medical oncologists, research nurses, pharmacists and biostatisticians with direct experience in cancer clinical research. Information that raises any questions about participant safety will be addressed with the Overall PI and study team.

The DSMC will review each protocol up to four times a year with the frequency determined by the outcome of previous reviews. Information to be provided to the committee may include: up-to-date participant accrual; current dose level information; DLT information; all grade 2 or higher unexpected adverse events that have been reported; summary of all deaths occurring within 30 days of intervention for Phase I or II protocols; for gene therapy protocols, summary of all deaths while being treated and during active follow-up; any response information; audit results, and a summary provided by the study team. Other information (e.g. scans, laboratory values) will be provided upon request.

13. STATISTICAL CONSIDERATIONS

13.1 Study Design, Objectives, and Endpoints

This is a prospective pilot study evaluating ¹⁸F-fluciclovine-PET/CT for detecting metastatic disease in patients with cT2-T4N0M0 muscle invasive bladder cancer.

The primary objective of this study is to estimate the agreement rate of metastatic disease status between ¹⁸F-fluciclovine-PET/CT and histopathology from radical cystectomy for detecting

locoregional metastatic disease in patients with cT2-T4N0M0 muscle invasive bladder cancer by conventional CT/MRI imaging. Secondary objectives include estimating of the rate of detection of suspected distant metastatic disease by ¹⁸F-fluciclovine-PET/CT, analysis of the association of ¹⁸F-fluciclovine uptake on PE/CT in primary bladder tumor with pathologic tumor grade/size after radical cystectomy, and analysis of ¹⁸F-fluciclovine uptake on PET/CT to the presence/absence of ASCT2 and LAT1 amino acid transporters in the resected primary bladder tumors.

The primary endpoints are metastatic disease status by ¹⁸F-fluciclovine-PET/CT and pathologic stage at radical cystectomy. The agreement rate is defined as the number of scans that are considered positive metastatic disease by both ¹⁸F-fluciclovine-PET/CT and histopathology and those considered negative metastatic disease by both ¹⁸F-fluciclovine-PET/CT and histopathology, out of all scans performed. A positive ¹⁸F-fluciclovine-PET/CT is defined as evidence of metastatic disease either regionally in the pelvic lymph nodes or distantly to bone, lungs, viscera, or lymph nodes outside of the pelvis. The ability of ¹⁸F-fluciclovine-PET/CT for detecting locoregional metastatic disease will be defined as the presence of disease detected locoregionally on ¹⁸F-fluciclovine-PET/CT. Secondary endpoints include visualization (present/absent) and number of distant metastases on ¹⁸F-fluciclovine-PET/CT. The amount of ¹⁸F-fluciclovine accumulation in the primary bladder tumor on PET will be quantified using the maximum standardized uptake value (SUVmax). Tumor grade/size and the presence of amino acid transporters will be assessed histopathologically with specimens from cystectomy as part of standard-of-care.

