1.2 Primary Objectives

To estimate the agreement rate of detecting metastatic disease between ¹⁸F-fluciclovine-PET/CT and histopathology from radical cystectomy for detecting locoregional metastatic disease in patients with cT2-T4N0M0 muscle invasive bladder cancer by conventional CT/MRI imaging.

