1.3 Secondary Objectives

1.3.1 To estimate the rate of detection of suspected distant metastatic disease by ¹⁸F-fluciclovine -PET/CT in patients with cT2-T4N0M0 muscle invasive bladder cancer by conventional CT/MRI imaging.

1.3.2 To investigate the relationship between ¹⁸F-fluciclovine uptake on PET/CT and pathologic tumor stage and size of primary bladder tumor after radical cystectomy.

1.3.3 To investigate the relationship between ¹⁸F-fluciclovine uptake on PET/CT and the presence/absence of a ASCT2 and LAT1 amino acid transporters in the resected primary bladder tumors.

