13.2 Data Analysis Plan

The primary and first secondary analyses will include all 16 eligible and treated patients with completed ¹⁸F-fluciclovine-PET/CT scans and pathology dissection. Among these 16 patients, those who undergo cystectomy will be included for secondary analysis 2 and 3.

We will tabulate the metastatic disease status by ¹⁸F-fluciclovine-PET/CT (limited to bladder, locoregional nodes positive, or distant) and pathologic stage at radical cystectomy and compute the agreement rate, along with the corresponding 90% exact binomial confidence interval (CI). The proportion of patients who show positive ¹⁸F-fluciclovine-PET/CT will be computed, along with the corresponding 90% exact binomial confidence interval. This similar methodology will be used to evaluate the proportion of agreement compared to histopathology and the rates of locoregional disease and suspected distant metastatic disease detected by ¹⁸F-fluciclovine-PET/CT. In addition, treating pathologic and/or biopsy findings as the reference standard, we will estimate the sensitivity and specificity of ¹⁸F-fluciclovine-PET/CT for detection of metastatic disease.

The analysis of the relationship of ¹⁸F-fluciclovine uptake on PET/CT (SUVmax) in primary bladder tumor to pathologic tumor grade/size after radical cystectomy will be analyzed using the Kruskal-Wallis test. The Wilcoxon-Rank-Sum test will be used to assess the association between SUVmax and the presence/absence of ASCT2 and LAT1 amino acid transporters in the resected primary bladder tumors.

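### The definition of a positive PET/CT includes distant sites, but the primary objective is locoregional agreement with cystectomy pathology, so distant-only scans are mis-scored in the 6/10 and 11/16 rules

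*Combined protocol and SAP*

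**What the plan says.** Section 1.2 sets the primary objective as the agreement rate between PET/CT and "histopathology from radical cystectomy for detecting locoregional metastatic disease"; 13.1 repeats it. Distant disease has its own place as the first secondary objective in 1.3: "To estimate the rate of detection of suspected distant metastatic disease by" PET/CT.

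Section 13.1 then makes three statements in sequence:

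- The rate itself: "The agreement rate is defined as the number of scans that are considered positive metastatic disease by both" PET/CT and histopathology, plus those negative by both, over all scans performed. No anatomical site is named.
- A positive PET/CT: "evidence of metastatic disease either regionally in the pelvic lymph nodes or distantly to bone, lungs, viscera, or lymph nodes outside of the pelvis".
- Locoregional detection by the scan, which "will be defined as the presence of disease detected locoregionally on" PET/CT.

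Section 13.2 cross-tabulates PET status in three levels against pathology: "limited to bladder, locoregional nodes positive, or distant) and pathologic stage at radical cystectomy and compute the agreement rate". It does not say which cells agree. The same section gives the broad definition a use of its own ("The proportion of patients who show positive" PET/CT, with a 90% interval). It brings in biopsy only for diagnostic accuracy: "treating pathologic and/or biopsy findings as the reference standard, we will estimate the sensitivity and specificity".

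Section 13.3 applies both cut-offs, 6 of 10 and 11 of 16, to agreement on metastatic disease status, without naming a site. Section 13.5 only refers back to 13.1.

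**The concern.** The two sides of the comparison do not cover the same anatomy. The reference is the surgical specimen, which according to 5.1 usually, but not always, includes a pelvic node dissection. No section schedules sampling of bone, lung or viscera, and extrapelvic nodes are covered only if the dissection happens to reach them. Under the definition in 13.1, however, uptake at any of those sites makes the scan positive.

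The scans affected are those with distant uptake and no pelvic nodal disease on PET, called distant-only here. The cystectomy specimen cannot confirm or refute what made such a scan positive, yet the scan enters the primary count as a hit or a miss according to the state of the pelvic nodes.

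At stake is the trial's declared result. Success is defined as 11 or more agreements among 16, a count small enough for a single scan to decide. Because the objective points to one scoring and the definition to another, an analyst who has seen the data could defend either.

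**Working it through.** **1. Reproduce the design in 13.3.** Inputs: 10 patients in stage 1, continue with 6 or more agreements; 16 in total, success with 11 or more; null rate 0.50, alternative 0.75. Let X1 be the stage-1 count and X2 the count among the next 6.

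- Early stop under the null: P(X1 ≤ 5 | 10, 0.50) = 638/1024 = 0.623 (stated 0.62).
- Success: the sum over x = 6 to 10 of P(X1 = x) × P(X2 ≥ 11 − x). This gives 0.101 at 0.50 (stated 0.101) and 0.800 at 0.75 (stated 79.9%).
- 90% exact interval at 12/16: 0.516 to 0.910 (stated 0.52, 0.91).

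The arithmetic is sound. The problem is which scans count as agreeing.

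**2. Score a distant-only scan under the two readings.**

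| Pelvic nodes at pathology | Literal 13.1 rule (PET positive) | Locoregional rule (PET negative) |
|---|---|---|
| Negative | disagree | agree |
| Positive | agree | disagree |

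The two readings give opposite scores in both rows. They agree on every other scan: one with pelvic nodal disease is positive under both, and one with no metastatic disease is negative under both. Hence

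locoregional count − literal count = n(distant-only, node-negative) − n(distant-only, node-positive).

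This needs no assumed rates. It is zero only when the two numbers are equal, and a single distant-only scan always shifts the count by one.

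**3. Effect at the cut-offs, with one distant-only scan.**

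- Literal 11/16 becomes 10/16 (success to failure) if the patient is node-positive.
- Literal 10/16 becomes 11/16 (failure to success) if the patient is node-negative.
- In stage 1, literal 6/10 becomes 5/10, or 5/10 becomes 6/10, in the same way.
- The estimate moves between 11/16 = 0.69 (90% exact CI 0.452 to 0.868) and 10/16 = 0.63 (0.391 to 0.822).

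**4. How often the count lies next to a cut-off.** Among the C(16,10) = 8008 arrangements with 10 agreements, those failing stage 1 number 210 × 1 (X1 = 4, X2 = 6) plus 252 × 6 (X1 = 5, X2 = 5) = 1722, leaving 6286. Among the C(16,11) = 4368 with 11 agreements, 252 fail (X1 = 5, X2 = 6), leaving 4116.

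| | Rate 0.50 | Rate 0.75 |
|---|---|---|
| Stage 1 passed, total = 10: 6286 p^10 (1−p)^6 | 0.0959 | 0.0864 |
| Stage 1 passed, total = 11: 4116 p^11 (1−p)^5 | 0.0628 | 0.1698 |
| Sum | 0.159 | 0.256 |
| X1 = 5: 252 p^5 (1−p)^5 | 0.2461 | 0.0584 |
| X1 = 6: 210 p^6 (1−p)^4 | 0.2051 | 0.1460 |
| Sum | 0.451 | 0.204 |

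These are chances of being one scan from a cut-off. They are not chances of a reversal, which also requires a distant-only scan in a patient of the right nodal status.

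**The case against.** The best defence takes one of two routes.

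The first is that 13.1 is not silent. It defines a positive scan, and 13.5 sends the primary analysis to 13.1, so a distant-only scan is simply positive and there is nothing to choose afterwards. That is a fair reading of the text. But it leaves a stated rule that gives the wrong score, for the stated objective, on exactly these scans.

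The second is that the locoregional reading is plainly intended. The objective says so, 13.1 goes on to define locoregional detection, distant detection is secondary, and 13.2 plans separate locoregional and distant rates. This has real support. However, the locoregional sentence in 13.1 neither redefines a positive scan nor mentions the agreement rate, and 13.2 lists agreement and the site-specific rates side by side without linking them. The three-level table would not settle the matter either, because its distant level does not separate distant-only scans from those with pelvic nodes as well. One could even match it category by category, in which case a distant-only scan disagrees with both node-negative and node-positive pathology. The opposite scoring shown above is therefore between the two main readings, and they are not the only possible ones.

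Some limits stand. Patients have no definite metastatic disease on conventional imaging (3.1.2), so distant-only scans may be few. The stage-1 rule is not binding, since 13.3 allows either stopping or amendment. This is a pilot whose primary aim is estimation. These points bear on how likely harm is. They do not remove the mismatch, and 13.3 still declares success at 11 of 16.

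**Conclusion.** The concern holds and should be corrected before the primary analysis. As written, the only definition of a positive PET/CT includes sites that the cystectomy specimen cannot verify. It credits PET with agreement in node-positive patients whose nodes it missed, and charges it with disagreement for distant lesions that may be real.

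The firm part of the size needs no assumptions: each distant-only scan changes the primary count by one between the literal and locoregional readings, and one is enough to cross 11/16 or 6/10. The probabilities of lying beside a cut-off assume the plan's own 50% and 75% rates. The documents give neither a distant-only rate nor a statement of whether 50% and 75% mean locoregional agreement, so the size and direction of any effect on power or type I error cannot be determined.

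**What to change.** In 13.1, 13.2 and 13.3, state that for the primary agreement rate and for both decision rules a positive PET/CT means pelvic (locoregional) nodal disease, compared with pathologic nodal status. A distant-only scan is then classed by its pelvic PET status, which must be recorded for every patient with distant uptake. The sponsor should confirm that the 50% and 75% rates refer to this count.

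Keep the regional-or-distant definition, labelled as such, for the overall proportion positive and for sensitivity and specificity for metastatic disease in 13.2. Report distant detection under secondary objective 1.

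A related, lesser point for the same amendment: 13.3 treats a patient without pathology dissection as unevaluable and replaced, while 13.7.2 counts everyone with PET/CT and radical cystectomy as evaluable. Since node dissection is only usual (5.1), the two should be reconciled for a patient with no nodes examined.

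The cost is a dated wording amendment and one per-patient field, which should be derivable from the lesion scoring in 5.4.2. No extra patients, scans or procedures are needed, and the sample size and cut-offs stand if the sponsor confirms the meaning of 50% and 75%. The reference in 13.3 to a further 16 months of accrual may mean enrolment has begun; if so, pelvic status must also be recorded for scans already called positive on distant uptake.
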